Appendix 1 Drugs of interest

Drug name	Drug type	Start dose	Target dose
Captopril	ACEi	6.25 mg three times daily	50 mg three times daily
Enalapril	ACEi	2.5 mg twice daily	10-20 mg twice daily
Lisinopril	ACEi	2.5-5 mg once daily	20-35 mg once daily
Perindopril	ACEi	2-4 mg daily	8 mg daily
Ramipril	ACEi	2.5 mg once daily	10 mg once daily
Trandolapril	ACEi	0.5 mg once daily	4 mg once daily
Candesartan	ARB	4-8 mg once daily	32 mg once daily
Eprosartan	ARB	600 mg once daily	-
Irbesartan	ARB	150 mg once daily	300 mg once daily
Losartan	ARB	12.5-50 mg once daily	150 mg once daily
Sacubitril/Valsartan (Entresto®)	ARB	49/51 mg twice daily	97/103 mg twice daily
Telmisartan	ARB	20–40 mg once daily	80 mg once daily
Valsartan	ARB	40 mg twice daily	160 mg twice daily
Eplerenone	MRA	25 mg daily	50 mg daily
Spirolactone	MRA	25 mg daily	50 mg daily

Sources: European Society of Cardiology (ESC) Guidelines for the diagnosis and treatment of acute and chronic heart failure, 2016. Available from <https://academic.oup.com/eurheartj/article/37/27/2129/1748921> and British National Formulary. Available from <https://bnf.nice.org.uk>

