Maximum tolerated dose: highest dose of RAASi (or MRA) recorded in medical records during observation period

Observation period: the 12 month period from index event

Target dose: as stated in medical records, national or international clinical guidelines or Summary of Product Characteristics (SPC) if not recorded in medical records (see Appendices)

Type 2 diabetes (T2DM): Chronic metabolic disorder that results in hyperglycaemia (high blood glucose levels) due to the body's inability to produce enough insulin or lack of ability to utilise the insulin being produced (insulin resistance). Confirmed diagnosis in medical records

4. Study synopsis

Title	
SoMoR – UK (Study of Management of RAASi in UK)
 
A multi-centre, retrospective observational study on renin-angiotensin-aldosterone system inhibitors (RAASi) management in patients treated for chronic kidney disease alongside heart failure and/or type 2 diabetes mellitus.

Background and rationale for study	
In order to improve renin-angiotensin-aldosterone system inhibitors (RAASi) treatment by increasing the proportion of patients who achieve target doses according to clinical guidelines, the maximum tolerated doses that are currently achieved need to be determined. This study will therefore describe the characteristics and treatment outcomes of patients with CKD and at least one of the following: heart failure (HF) and/or type 2 diabetes mellitus (T2DM) and who receive RAASi in the real world UK NHS setting but do not achieve target dose. The maximum tolerated doses achieved by these patients and the length of time on these doses will be reported.

Objectives	
Primary objective
 
 1. To describe doses of RAASi prescribed to patients with CKD in the UK NHS setting 
Secondary objectives
 
 1. To describe doses of mineralocorticoid receptor antagonist (MRA) prescribed to patients with CKD and HF 2. To describe other drug types concomitantly prescribed for CKD and/or HF in patients treated with RAASi 3. To describe clinical outcomes associated with RAASi treatment 4. To describe the demographic and clinical characteristics of patients treated with RAASi and do not achieve target dose, at initiation of treatment
Hypothesis statement	
This is a descriptive study and therefore an a priori hypothesis will not be tested.

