6.1 Rationale for study

In order to improve RAASi treatment in terms of increasing the proportion of patients who achieve target doses according to clinical guidelines, the maximum tolerated doses that are currently achieved need to be determined. This study will therefore describe the characteristics of patients with CKD (and at least one of the following: HF and/or T2DM)

who are treated with RAASi but do not achieve target dose. The maximum tolerated doses achieved by these patients and the length of time on these doses will be reported.

7. Aim and objectives

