9.2 Study population

The study will include adult patients with CKD stage 3 or 4 who do not achieve target dose of RAASi and have at least one of the following:

- heart failure (HF)
- type 2 diabetes mellitus (T2DM)

Where:

- CKD stage 3 or 4 is defined as estimated glomerular filtration rate (eGFR) $>14\text{ml}/\text{min}/1.73\text{m}^2$ and $<60\text{ml}/\text{min}/1.73\text{m}^2$
- HF is defined as presence of reduced ejection fraction and left ventricular ejection fraction (LVEF) $<40\%$
- T2DM is defined as a confirmed diagnosis in medical records
- Target dose is defined as recorded in medical records, or Summary of Product Characteristics (SPC) if not recorded in medical records (see Appendices)

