9.2.1 Inclusion criteria

- Diagnosed with CKD stage 3 or 4 and at least one of the following: HF and/or T2DM
- Prescribed a RAASi for the first time at an outpatient CKD and/or HF clinic between 01 January 2016 to 31 December 2016 ('the enrolment period')
- Aged ≥ 18 years when prescribed a RAASi for the first time during the enrolment period

- Patients who do not achieve target dose of RAASi during the observation period
- With ≥ 12 months follow up data during the observation period
- Consent to researcher access to their medical records for study data extraction (living patients only)

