9.5.1 Primary endpoint

The primary endpoint of this study is the mean maximum tolerated daily dose of RAASi achieved (as percentage of target dose).

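### Where the medical record states no target dose, the fallback that sets both eligibility and the primary endpoint's denominator is contradictory and not single-valued

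*Protocol*

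**What the plan says.** The primary endpoint (Protocol, Section 9.5.1) is the "mean maximum tolerated daily dose of RAASi achieved (as percentage of target dose"). The inclusion criteria (Section 9.2.1) use the same quantity as a threshold: "Patients who do not achieve target dose of RAASi during the observation period".

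Target dose is described in four places:

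- Section 3, List of definitions: "as stated in medical records, national or international clinical guidelines or Summary of Product Characteristics (SPC) if not recorded in medical records", with a pointer to the appendices.
- Section 9.2, Study population: "Target dose is defined as recorded in medical records, or Summary of Product Characteristics (SPC) if not recorded in medical records", with the same pointer. Guidelines are not named.
- Section 6.1, Rationale: the purpose is "increasing the proportion of patients who achieve target doses according to clinical guidelines".
- Appendix 1 lists the doses. Its sources are the "European Society of Cardiology (ESC) Guidelines for the diagnosis and treatment of acute and chronic heart failure, 2016" and the British National Formulary. The SPC is not among them.

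In Appendix 1 the target for enalapril is "10-20 mg twice daily" and for lisinopril "20-35 mg once daily". Eprosartan has a start dose but a dash in the target column. The other ten of the 13 listed RAASi have one target value each.

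Table 2 (Section 9.5.3) collects drug name, dose and start date for RAASi prescriptions. It has no variable for the target dose applied.

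**The concern.** A quantity that decides both who enters the study and what each patient contributes to the primary endpoint needs one value per patient, reached by one route. Sections 3 and 9.2 agree on the first step, the medical record, and part company on the second. The table meant to supply the second step comes from sources that Section 9.2 does not name, and for three drugs it does not give one number.

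A care team screening a patient with no recorded target can therefore follow the protocol and reach either of two answers on eligibility. For a patient who is eligible on either answer, the percentage entered in the mean still depends on the reading. With five to ten centres, different readings may produce differently selected patients and percentages on different scales. Because the data set as listed does not hold the target used, the difference could not be traced at analysis.

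**Working it through.** **Inputs.** Appendix 1: enalapril target 10 to 20 mg twice daily, i.e. 20 to 40 mg per day; lisinopril target 20 to 35 mg per day; start doses 2.5 mg twice daily and 2.5–5 mg daily respectively. Section 9.2.1: eligible only if target is not achieved. All results below are for a patient with no target in the medical record.

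**Formula.** Percentage of target = daily dose / daily target × 100; eligible if below 100%.

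**Prescriptions whose eligibility flips**

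- Enalapril 10 mg twice daily: 20/20 = 100% on the lower end, ineligible; 20/40 = 50% on the upper end, eligible.
- Lisinopril 20 mg daily: 20/20 = 100%, ineligible; 20/35 = 57.1%, eligible.

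**Prescriptions eligible either way, with a different percentage**

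- Enalapril 5 mg twice daily: 10/20 = 50% or 10/40 = 25%, a gap of 25 points.
- Lisinopril 10 mg daily: 10/20 = 50% or 10/35 = 28.6%, a gap of 21.4 points.
- Enalapril 2.5 mg twice daily: 5/20 = 25% or 5/40 = 12.5%, a gap of 12.5 points.
- Lisinopril 5 mg daily: 5/20 = 25% or 5/35 = 14.3%, a gap of 10.7 points.

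**Eprosartan.** Appendix 1 alone gives neither a percentage nor an eligibility decision.

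**Effect on the overall mean (illustration only).** The protocol gives no drug mix, no dose distribution and no share of patients with a recorded target. Assume a share s of the sample takes the two ranged drugs, none has a recorded target, all take the same dose, and the sample is the same under both readings. The shift is then s × gap.

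- s = 10%, at start doses: 0.10 × 10.7 = 1.1 (lisinopril 5 mg) to 0.10 × 12.5 = 1.3 points (enalapril).
- s = 10%, at half the lower-end target: 0.10 × 21.4 = 2.1 (lisinopril) to 0.10 × 25 = 2.5 points (enalapril).
- s = 30%, all on enalapril 5 mg twice daily: 0.30 × 25 = 7.5 points.

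These are examples, not bounds. Letting the sample change, as it would, alters the result. With equal numbers on enalapril 5 mg and 10 mg twice daily, the lower end keeps only the first group (mean 50%), while the upper end keeps both: (25 + 50)/2 = 37.5%. That subgroup moves by 12.5 points rather than 25.

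For scale, the half-widths in Table 3 (Section 11) at 100 patients run from 3 points (47% to 53%) to 6 points (84% to 96%).

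**The case against.** The best defence is that the problem is narrow. Ten of the 13 RAASi have a single target, so the ranges touch two drugs of unknown frequency, and only when the record is silent. A guideline-based appendix fits Section 3; only Section 9.2 is out of line, and whether formulary and SPC values differ cannot be checked from the protocol. Reaching the lower end of a range is a natural reading of having achieved target. Section 10.2 also provides data collection guidelines, programmed eligibility checks and a pilot, and an SAP is promised.

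Much of this stands as to size. It does not remove the defect. The natural reading is not written down, and even if it settles eligibility it leaves the denominator below the range open. Nor can the matter simply be left to the SAP: the care team identifies eligible patients (Section 9.2.3), whereas Section 12 requires the SAP only by the end of data collection. Neither a later rule nor the checks in Section 10.2 would recover a patient already screened out.

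A reader might infer three stronger points that the protocol does not support:

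- *That putting the medical record first is itself an error.* It can give two patients on the same drug and dose different percentages, but Sections 3 and 9.2 agree on it. It is a design choice.
- *That the endpoint cannot be computed for eprosartan.* A target may still come from the record or the SPC, and under Section 3 from a guideline. The dash blocks the calculation only if Appendix 1 is the sole fallback.
- *That the mean is shown to move by as much as Table 3's precision.* Any such figure rests on assumed drug shares, doses, absence of recorded targets and a fixed sample, and at the low end it falls below 3 points.

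**Conclusion.** The concern holds for patients with no target in the medical record. Sections 3, 9.2 and Appendix 1 do not define one fallback, and for enalapril and lisinopril the appendix gives a range where one number is needed. The classification results are exact given Appendix 1: 100% or 50% for enalapril 10 mg twice daily, and 100% or 57% for lisinopril 20 mg daily, with eligibility changing in step. A patient read as 100% is excluded rather than averaged in, so these pairs describe how one prescription is classified, not a movement of the mean.

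The effect on the overall mean is not determinable. About 1 to 7.5 points is an illustration under the assumptions stated with the calculation. The point matters because it affects both selection and the primary endpoint, and because selection cannot be repaired at analysis. No view is taken on which dose is right.

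**What to change.** Before screening, the sponsor and chief investigator should:

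1. Reconcile Sections 3, 9.2 and Appendix 1 into one source order for patients without a recorded target, and make the sources cited in the appendix match it.
2. Set one single-valued fallback denominator per drug, of their choosing, and use it for both eligibility and the primary endpoint.
3. State how a listed drug without a value is handled.
4. Since the record-first rule is kept, add to Table 2 a field for the target used and its source.
5. Report a sensitivity analysis of the primary endpoint using the common fallback value for every patient on that drug. Some percentages there may reach or exceed 100%, because eligibility was judged on a recorded target; they should be kept and reported.

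The cost is a short amendment to two definitions and one appendix table, one added data field, and one further analysis.

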1	21 st March 2018	References to mineralocorticoid receptor antagonists (MRAs) updated in the following sections: 3. List of definitions (page 8), 4. Study synopsis (pages 9 and 11), 6. Background (page 15), 7. Aim and objectives (page 16), 9. Study design and methodology (pages 20 and 23).	Only spironolactone was previously included in the protocol but data on eplerenone will also be collected in the study.
2	21 st March 2018	Removal of exclusion criteria for "Received dialysis during the observation period". The following sections have been updated: 4. Study synopsis (page 11) 9. Study design and methodology (page 18).	Although very few patients with CKD stage 3 or 4 (study population of interest) will receive dialysis, excluding these patients may introduce bias and therefore they should not be excluded from the study.
3	21 st March 2018	Secton 17. Study timelines updated (page 31).	Updated as timelines for study activities (but not study completion date) have changed since the last version of the protocol in December 2017.

6. Background and rationale

It is estimated that approximately 6% of the population of England aged 16 years or older have (diagnosed or undiagnosed) chronic kidney disease (CKD) stage 3 to 5¹. Renin–angiotensin–aldosterone system inhibitors (RAASi) are commonly prescribed to patients with CKD, with or without heart failure (HF) and with or without diabetes mellitus. RAASi include the following drug types: angiotensin converting enzyme inhibitors (ACEi) and angiotensin receptor blockers (ARBs).

RAASi are used to delay disease progression (e.g. end-stage renal failure) and to prevent major cardiac events. As such, they can maintain/improve and prolong patients' quality of life. The introduction and maintenance of RAASi treatment is well established as part of recommended treatment pathways for CKD and HF^{2–4}. However, patients treated with RAASi are at risk of elevated serum potassium levels (hyperkalaemia), through impaired renal function and/or side effect of the drugs. As hyperkalaemia can be a serious medical emergency, leading to organ failure and resulting in death, patients often do not achieve the target doses that are required for optimal clinical benefit due to clinician concerns about potential, or actual episodes of, hyperkalaemia^{5–7}. Patients with HF are typically also treated with a mineralocorticoid receptor antagonist (MRA), such as spironolactone or eplerenone.

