9.5 Study endpoints and variables

Results will be presented by RAASi drug type, i.e. angiotensin-converting enzyme (ACE) inhibitors and angiotensin II receptor blockers (ARBs), and patient group (CKD and HF, CKD and T2DM, CKD and HF and T2DM), where appropriate. Patient-level data will be collected from each centre for the following endpoints during the observation period.

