9.5.2 Secondary endpoints

The following endpoints will also be measured:

Prescribing modalities, including concomitant prescribing

- Length of time on maximum tolerated daily dose of RAASi
- Proportion of patients with HF who receive RAASi and MRA

- Maximum tolerated daily dose of MRA achieved in patients with HF
- Length of time on maximum tolerated daily dose of MRA in patients with HF
- Distribution of other drugs concomitantly prescribed for CKD and/or HF in patients treated with RAASi, by drug type

Clinical outcomes

- Proportion of patients with elevated serum potassium level (>5.1 mmol/L, >5.5 mmol/L or >6.0 mmol/L) during the observation period
- Number of episodes per patient with elevated serum potassium level (>5.1 mmol/L, >5.5 mmol/L or >6.0 mmol/L)
- Change in mean serum potassium level (from index date to last result during observation period)
- Change in mean serum creatinine level (from index date to last result during observation period)
- Change in mean urine protein level (from index date to last result during observation period)
- Change in mean blood pressure level (from index date to last result during observation period)
- Proportion of patients who stop RAASi treatment at least once during the observation period
- Reason(s) for changing RAASi dose or stopping RAASi treatment, where relevant

The following patient characteristics will also be included in analyses:

- Age at index event
- Sex
- Ethnicity
- HF status
- Comorbidities documented at baseline
- Length of time since diagnosis of CKD (and HF and/or T2DM, if relevant) at index event
- eGFR at baseline

- LVEF at baseline, if diagnosed with HF

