Between-group differences (for drug type and patient group) will be evaluated by unpaired t-tests, Wilcoxon rank-sum test or chi-square test, as appropriate. Within-group differences will be assessed by paired sample t-test, Wilcoxon matched-pairs signed-ranks test or McNemar test, as appropriate. 95% confidence intervals will be presented for estimates of proportions and means of distributions, as appropriate. Additional statistical tests may be applied, as appropriate to the data. Statistical analyses will be carried out using Stata version 14 (StataCorp LLC) and Microsoft Excel™ 2010. A technical overview of study reporting will be provided in a statistical analysis plan (SAP) before data collection is completed.

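### Sacubitril/valsartan is classed as an ARB, so the ARB results and the ACEi versus ARB tests mix ARB-only with combination treatment

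*Protocol*

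**What the plan says.** Section 6 of the protocol defines the class by two drug types: "RAASi include the following drug types: angiotensin converting enzyme inhibitors (ACEi) and angiotensin receptor blockers (ARBs". Appendix 1 then assigns a type to each drug. The row for "Sacubitril/Valsartan (Entresto"®) carries the type ARB and a two-part target dose, "97/103 mg twice daily". Valsartan alone appears in a separate row, also typed ARB.

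Section 9.5 uses these types as reporting strata: "Results will be presented by RAASi drug type, i.e. angiotensin-converting enzyme (ACE) inhibitors and angiotensin II receptor blockers (ARBs"), alongside patient group and where appropriate. Section 12 adds formal comparisons: "Between-group differences (for drug type and patient group) will be evaluated by unpaired t-tests, Wilcoxon rank-sum test or chi-square test".

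The endpoints include dose as a percentage of target (section 9.5.1) and, in section 9.5.2, potassium, creatinine, urine protein, blood pressure and stopping of RAASi. Nowhere does the protocol set a separate category, an exclusion or a sensitivity analysis for the combination product.

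**The concern.** The appendix itself shows that the product is valsartan plus a second component. A stratum labelled ARB that contains it is therefore not a stratum of ARB-only treatment. If ARB and ACEi patients differ in potassium, creatinine, blood pressure or stopping, a reader of the by-type tables cannot tell whether the difference belongs to ARBs or to the combination.

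About 100 patients are planned in total, so the ARB stratum will be smaller than that, and a few combination users could carry visible weight in it. What is at stake is the interpretation of the by-drug-type tables and tests, not the main result.

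**Working it through.** No figure in the protocol depends on this label, so there is none to reproduce. The check has two parts.

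**1. Does following the protocol pool the product with ARBs?**

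- Section 6 names two RAASi drug types. Its verb (include) could leave room for others.
- Section 9.5 removes that room: it spells out drug type as ACE inhibitors and ARBs and names no third type.
- Appendix 1 places the combination in the ARB type.
- Section 12 compares drug types, which for RAASi means ACEi against ARB.

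Read together, these put the combination into the ARB column and into the ACEi versus ARB tests. The protocol has made this classification; it has not left it open.

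**2. What would the pooling do to a result?**

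Let w be the share of the ARB group taking the combination, and D the difference in mean between combination users and other ARB users.

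- ARB mean = (1 − w) × mean(other ARB) + w × mean(combination) = mean(other ARB) + w × D
- The ARB mean therefore shifts by w × D, and the ACEi–ARB contrast changes by the same amount. A proportion, such as patients who stop treatment, mixes in the same way.

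The protocol gives neither w nor D. The values below are assumptions for illustration only, in whatever unit the endpoint uses:

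| w (assumed) | D = 5 units | D = 10 units |
|---|---|---|
| 5% | 0.05 × 5 = 0.25 | 0.05 × 10 = 0.5 |
| 20% | 0.20 × 5 = 1.0 | 0.20 × 10 = 2.0 |
| 40% | 0.40 × 5 = 2.0 | 0.40 × 10 = 4.0 |

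If D is zero or there are no users, the shift is zero. The table shows the mechanism; it does not estimate this study's effect.

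**Where the label has no effect.** The primary endpoint, the "mean maximum tolerated daily dose of RAASi achieved (as percentage of target dose"), is summarised over all RAASi patients. Moving the product between types leaves that overall mean unchanged. Only the by-type breakdown changes.

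**The case against.** The strongest reply has four parts.

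- **Flexibility.** Reporting by drug type is qualified as where appropriate, Table 2 records the drug name for every RAASi prescription, and section 12 promises an SAP. The product could be separated later without new data. This is true and keeps the point minor. It does not remove it, because an SAP that follows the protocol's own type column and two strata would pool the product.
- **No effect size.** Distortion needs both a meaningful number of users and a different response. The protocol supplies neither and does not describe what the second component does. This stands in full.
- **Descriptive study.** There is no a priori hypothesis, and the sample size was set by the precision of the overall mean. This also stands, although section 12 still plans between-type tests.
- **Patient group.** A reader might infer that the combination is used mainly in heart failure, so that drug type becomes confounded with patient group. Appendix 1 cites a heart failure guideline, but the protocol says nothing about who receives the product, and patient group is already a reporting stratum. This remains an assumption.

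A reader might also infer a distortion of the dose endpoint. The documents do not support either form of that argument:

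- The combination's target contains 103 mg of valsartan against 160 mg for valsartan alone (103/160 = 64%), which might look like two scales for one drug. That reading assumes that milligrams are interchangeable between the two products, which the protocol never states. Each product is scored against its own target, and section 3 takes the target from the medical record first.
- The listed start dose of the combination is about half its target (51/103 = 49.5%), so unadjusted starters would raise the ARB mean. With 5 of 20 ARB patients at 50% and 15 at 25%, the mean is (15 × 25 + 5 × 50)/20 = 31.25%. But irbesartan also starts at 150/300 = 50% and would give exactly the same mean. Start-to-target ratios vary across ARBs in any case: candesartan 4–8/32 = 12.5–25%, telmisartan 20–40/80 = 25–50%. The shift reflects that variation, not the ARB label.

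**Conclusion.** The point holds as a labelling matter with limited reach. Appendix 1, section 9.5 and section 12 together place a two-component product in the ARB stratum. The by-drug-type results, above all potassium, creatinine, blood pressure and stopping, would then describe a mixture of ARB-only and combination treatment.

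The size is w × D with both terms unknown, so it may be small or nil. For dose, scoring each product against its own target softens the mixing, and no numerical distortion can be shown from the protocol's figures. The all-patient primary endpoint and the sample size are unaffected. It is a worthwhile tidy-up, not a threat to the study's main result. It rests on the by-type tables and tests being produced as the protocol describes them.

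**What to change.** - In section 6, section 9.5 and the type column of Appendix 1, list sacubitril/valsartan as a separate RAASi drug type. The edit to section 6 is needed so that the product's status as a RAASi stays clear.
- Report it descriptively in its own column.
- Run the ACEi versus ARB comparisons without it, or with and without it.
- Keep it in the all-patient primary endpoint.

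The cost is short edits in three places and one extra table column. No new data are needed, because drug name is already recorded. The ARB stratum loses a few patients, and the third column may be very small, which is a reason to keep it descriptive. No dose or clinical rule changes.
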